4.6 LABORATORY ASSESSMENTS

- ◆ Samples will be stored under the Human Tissue Act license and will be stored at Barts Health NHS Trust temporarily before being shipped to Charterhouse Square (Queen Mary University of London) and Biocentre South for more permanent storage.
- ◆ The amount of blood to be sampled in the study (up to 50 ml where applicable) is not considered significant in adult subjects.

Location of sample analysis is not determined and will vary from project to project. Appropriate material transfer agreements will be in place prior to transferring material for analysis to approved laboratories.

The purpose of this consenting project (the now completed pilot and the current extended study) is to gain consent to allow researchers, educationalists and clinicians preparing audits to rightfully access clinical data, to allow future contact for follow-up or recruitment into new research studies, taking and storing biological material (blood, saliva, throat, buccal and/or nasopharyngeal swabs, urine, faeces and any other biological samples available plus relevant human soft/solid tissue samples and to allow more detailed analysis of existing clinical data (e.g. MRI, ultrasound, echocardiogram, electroencephalogram or similar monitoring/measuring modalities).

At this time, outside the routine clinical pathology indicated for each patient, no specific laboratory assessments have been planned. Blood, saliva, throat, buccal and/or nasopharyngeal swabs, urine, faeces and any other biological samples available, plus human soft/solid tissue samples, donated for this research project can be analysed in the future without repeat consent similar to the approach taken in UK Biobank (www.ukbiobank.ac.uk) and the NIHR BioResource. As described in the ethical issues section above, clinically relevant findings made by these laboratory tests will be fed back to the patients according to the duty of care to our patients.

Development of this protocol for the collection of biological samples was led by a number of key principles. In particular, the aim should be to collect samples that would allow the widest possible range of assays that could plausibly be envisaged for the future, and to avoid collection, processing or storage approaches that would inherently preclude such assays (i.e. “future proof” the collection as far as possible given current knowledge and available resources).

The coordinating centre laboratories Standard Operating Procedures will detail the samples to be collected, the preliminary processing and storage temperatures, the

transport of samples to a central processing facility, and the processing, aliquoting and storage of each sample (including barcoding).

4.7 END OF STUDY DEFINITION

Initial Pilot:

The 3- month pilot study informed the logistics required to extend the study. We moved stepwise to the extended study as resources could be identified based on the information provided by the initial pilot study, adding additional patient pathways for recruitment. If changes to the protocol were required, an amendment would be submitted to the ethics committee. If no changes to the protocol were required, Barts Health R&D (Operational group) would sign off any extension to additional patient pathways, if feasibility is likely, i.e. sufficient human and financial resources are available to perform the study and if of sufficient scientific priority.

Extended study:

The current intention of the study is to recruit patients for 10 years (if extended we will apply for major amendment). Samples will be stored for a minimum of 10 years. The end of the study is thus after 20 years; although subject to revision with regulatory approvals.

4.8 PROCEDURES FOR UNBLINDING

Not applicable.

4.9 SUBJECT WITHDRAWAL

Subjects will be withdrawn from the **Barts BioResource** if the subject withdraws consent. Withdrawal procedures reflect the types of withdrawal outlined in [Section 3.4](#).

4.10 DATA COLLECTION AND FOLLOW UP FOR WITHDRAWN SUBJECTS

See [Section 4.9](#)

The options for withdrawal will be fully explained:

“No further contact”: This means that **Barts BioResource** team would no longer contact the participant directly, but would still have their permission to use information and samples provided previously and to obtain further information from their health-relevant records.

“No further access”: This means that **Barts BioResource** team would no longer contact the participant or obtain information from their health-relevant records in the future, but would still have their permission to use the information and samples provided previously.

“No further use”: This means that, in addition to no longer contacting the participant or obtaining further information, **Barts BioResource** team would aim to destroy all of their information and samples collected previously (although the participant would be told that it may not be possible to trace all distributed sample remnants for destruction). Such a withdrawal would prevent information about them from contributing to further analyses, but it would not be feasible to remove their data from analyses that had already been done.

These patients will be removed from any data registry relating to the **Barts BioResource** and any donated samples stored in house will be destroyed in accordance with our Standard Operating Procedures.}

In relation to patients who are incapacitated at their time of recruitment, their Next of Kin (NOK) may also direct the “No further use” option which will be respected and acted on in accordance with our Standard Operating Procedures.

Donated samples stored at the long term sample storage supplier will be destroyed in accordance with the SOP.

5.0 LABORATORIES

See also [Section 4.6](#)

5.1 CENTRAL/LOCAL LABORATORIES

Associated BBR delivery organisation laboratories used for the short-term storage of tissue and biological samples will be subject to Standard Operating Procedures and the HTA licence held by Barts Health NHS Trust.

Laboratories used for the long-term storage of tissue and biological samples will be subject to the supplier’s Standard Operating Procedures and HTA licence.

Type and location of sample analysis is not determined for the Barts **BioResource**. As per access procedures specific research projects will determine the most cost-effective and appropriate laboratory for analysis and samples will not be released until the Barts Health NHS Trust approved Material Transfer Agreement has been signed by all parties.

5.2 SAMPLE COLLECTION/LABELLING/LOGGING

Collection of Blood Samples

Barts BioResource personnel will follow detailed Standard Operating Procedures for processing, logging and storage of samples, including adverse event standard procedure and reporting. A blood sample (up to 50 ml) will be obtained from all consented individuals by a nurse/ technician trained in cannulation and venepuncture. A summary of the blood processing procedure is provided in Figure 2 below.

Up to 50mls of blood will be collected into aliquots. These will include 2x 4.5ml EDTA, 1x 5ml PST, 2x 5.0ml STT/gel, up to 2x 2.5ml PAXgene for RNA and a 20 ml “floating” sample. The floating sample will be available and processed for specific projects in accord with access applications approved by the Barts Heart Centre peer review committee. Blood will undergo on-site processing and samples will be aliquoted into bar coded cryovials as follows: EDTA (plasma) to 9 cryovials, EDTA (white cells) to 2 cryovials, LH (PST) up to 4 cryovials, SST up to 8 cryovials, PAXgene RNA to up to 10 cryovials (Figure 2).

Each cryovial will be individually logged into the Barts [BioResource](#) database (LIMS) by research staff using a bar-code reader and then stored in a secure location on-site in an appropriate freezer aligned to the appropriate management of the samples obtained (e.g. -20°C, -40°C or -80°C freezers). Samples will be collected on an approximately monthly basis by secure courier and transported on dry ice for long term storage with a 3rd party supplier where they will be stored at an appropriate temperature until they are retrieved for analysis, which may be up to 20 years after sampling.

Samples will be stored with the National Biosample Centre (‘biocentre’) under contract with the Sponsor and/or its delivery partners to access the logistical requirements before a long-term solution is confirmed (Figure 3).

Residual tissue will be collected on a case-by-case basis according to routine pathology practice.

[figure not shown]

Figure 1: Summary of an Example Standard Operating Procedure (SOP) for Business As Usual processing and on-site short term storage of research biological samples (blood, saliva, throat, buccal and/or nasopharyngeal swabs, urine, faeces, soft/hard tissues and any other biological samples available).

[figure not shown]

Figure 2: Summary of logistics pathway for sample storage and transfer.

Labelling of all study biological materials:

- Subject Number
- Date of Collection
- Sampling Time (nominal)
- Protocol No.

All samples collected within this protocol will be recorded on a Laboratory Management Information System, which will further record subsequent patient consent, tracking and tracing of samples, temperature control of samples and locations

Short-term sample storage facilities will be within associated Barts BioResource delivery organisations and samples will be stored until collection by long-term storage supplier.

Long-term storage and management of biological samples

Samples will be appropriately sent to the party or parties contracted to handle the samples for extraction of biological material e.g. extraction of RNA or analysis e.g. for

circulating biomarkers at the appropriate time and will be carried out in accordance with the analytical plan agreed with the Chief Investigator.

5.3 SAMPLE RECEIPT/CHAIN OF CUSTODY/ACCOUNTABILITY

For both short-term and long-term sample storage handling of the samples upon arrival at the laboratory will to be documented. Upon receipt of the samples, the laboratory should ensure that the physical integrity of these samples have not been compromised in transit. If any damage has occurred or the samples have been compromised in any way it is important that the study team, as well as the Sponsor, are informed of this immediately. Upon receipt of samples laboratory staff should ensure that all samples are accounted as per the labelling. All samples received should be logged in an accountability log.

5.4 TISSUE MANAGEMENT AND ANALYSIS

UK Biobank's sample handling studies have demonstrated that maintaining whole blood samples at 4°C for at least 36 hours prior to processing and cryopreservation allows a very wide range of assays to be performed.

All tissue donated and collected for the protocol will be accessed only for the purposes outlined in this protocol and linked protocols as approved by Research Ethics Committees.

Samples will be tested until completely utilised, however, any residual derivative materials (such as cell culture and histological samples) will be discarded following completion of the various assays and where this is no further scientific value in their continued storage

Storage of the samples will be undertaken within the reference and definition of the Human Tissue Act 2004.

The *Chief Investigator* and designated deputies will oversee and audit the process of materials transfer and distribution to the recipient groups within the Barts Health NHS Trust and research groups within Queen Mary, University of London (such as The William Harvey Research Institute). Transfer and distribution to partner organisations with the UK, Europe and Worldwide will occur in accordance to documented materials transfer agreements.

5.5 SAMPLE ANALYSIS PROCEDURES

This protocol was led by a number of key principles. The bioresource aims to collect samples allowing the widest possible range of assays that could plausibly be envisaged for the future, and to avoid collection, processing or storage approaches that would inherently preclude such assays (i.e. "future proof" the collection as far as possible given current knowledge and available resources).

Sample Type	Selection Criteria
Blood	
 • Variety of fractions: plasma, serum, white cells, red cells, peripheral blood lymphocytes • Wide range of biomolecules: DNA, RNA [5' ends], proteins, analytes • Wide physiological coverage: genome, proteome and metabolome, haematological parameters • Suitable for a very wide range of assay technology • Ease and low cost of collection
Saliva, throat, buccal and/or nasopharyngeal swabs	
 • Wide range of biomolecules: DNA, RNA, proteins, lipids • Wide physiological coverage: genome, proteome • Suitable for microbial/fungal/viral species detection, biomarkers • Suitable for a wide range of assay technology • Ease and low cost of collection
Urine and faeces	
 • Range of biomolecules: DNA, protein • Physiological coverage: metabolomics, biomarkers, hormones, ions • Suitable for a wide range of assay technology • Ease and low cost of collection
Soft/solid tissue samples	
 • Biomolecules: DNA, RNA [5' ends], proteins, analytes • Wide physiological coverage: genome, proteome and metabolome • Suitable for a very wide range of assay technology • Research samples will be collected following clinical biopsy (if performed) and only if minimal risk to patient.

5.6 SAMPLE STORAGE PROCEDURES

Samples will be stored according to GCP and the Barts Health NHS Trust Tissue Bank policies.

5.7 DATA RECORDING/REPORTING

All study-related data will be recorded on CRF documents and/or electronically according to GCP standards and Barts Health NHS Trust policies.

The programme will also be used to develop, assess and validate the PowerTrials™ management system for research (Appendices 10-13).

6.0 PHARMACOVIGILANCE

Not applicable to current protocol has no treatment or therapy is a consequence of planned actions.

6.1 GENERAL DEFINITIONS

6.1.1 Adverse Event (AE)

During any clinical study, onset of Adverse Events may occur. An AE is defined as any untoward medical occurrence in a patient or clinical investigation subject administered a pharmaceutical product or intervention and that does not necessarily have a causal relationship with this treatment (where 'treatment' includes also all investigational agents such as comparative agents and placebo). An adverse event can therefore be any unfavourable and unintended sign, symptom, or disease.

All adverse events encountered during the clinical study are to be reported on the Adverse Event Forms contained in the Case Report Form (CRF). For each adverse event which occurs during the clinical study the Principal Investigator will give a judgment on its severity and make a causality assessment of the treatment using one of the four given definitions: certainly related, probably related, possibly related and definitely unrelated. Moreover, the Principal Investigator will indicate the action to be taken for the adverse event that has occurred and its outcome.

In the case of an adverse event, the trained medical personnel will act with appropriate diagnostic and therapeutic measures until the subject has recovered. Adverse events will be classified as 'serious' and 'non serious'. All this information will be recorded for each adverse event on the Adverse Event Form of the CRF. Detailed information on the compilation of the Adverse Event Form is available in [Appendix 1](#).

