4.5 FOLLOW UP PROCEDURES

This section applies to **both the Initial Pilot and the Extended study protocol:**

- Certain sub-studies may require follow-up via phone if patients agreed to be contacted in the future (separate ethics approval will be sought).
- Review routine medical and other health-related records both within the hospital and externally as required.

- Information via Central Registries and Data Controllers (such as hosted by NHS Digital, HQIP/NICOR and others including primary care data, Hospital episodes statistics (HES), and death registry formerly via Office for National Statistics, ONS).
- Information from GPs or their central registries if available.

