6.1.2 Serious Adverse Event (SAE)

An SAE fulfils at least one of the following criteria:

- Is fatal – results in death (NOTE: death is an outcome, not an event)
- Is life-threatening
- Requires in-patient hospitalisation or prolongation of existing hospitalisation
- Results in persistent or significant disability/incapacity
- Is a congenital anomaly/birth defect
- Is otherwise considered medically significant by the Investigator

Serious adverse events will be reported to the Principal Investigator and the Sponsor (see [Section 6](#)) within 24 hours. The 24 hours emergency contact numbers are listed on page iii of this protocol.

Serious adverse events will also be reported to:

- Barts Health NHS Trust, School of Medicine and Dentistry, Joint Research Office.

- National Research Ethics Service (NRES) approved Research Ethics Committee (the responsibility of the investigator) as soon as possible, but in any case, within 72 hours.

All available information will be provided, referring to the Serious Adverse Event paragraph of the Reporting Adverse Events document ([Appendix 1](#)). The Investigator will complete the Serious Adverse Event Form by carefully following the relevant instructions ([Appendix 1](#)) and will fax it within 24 hours to the Sponsor.

The Investigator, and others responsible for subject care, should institute any supplementary investigations of serious adverse events based on their clinical judgment of the likely causative factors. This may include seeking further opinion from a specialist in the field of the adverse event.

The Sponsor may also request extra tests. Continuation of the trial will be contingent upon approval from an independent safety review Committee.

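### Section 6 keeps drug-trial adverse-event wording: capture is not tied to a research procedure or a time window, the applicability rules conflict, and causality is graded against a treatment this registry does not give

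*Protocol*

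**What the plan says.** **What is captured.** Protocol 6.1.1 says "All adverse events encountered during the clinical study are to be reported on the Adverse Event Forms contained in the Case Report Form (CRF"). The definition in the same section reads "An AE is defined as any untoward medical occurrence in a patient or clinical investigation subject administered a pharmaceutical product or intervention", and adds that the event "does not necessarily have a causal relationship with this treatment". No start, stop or post-procedure period is given.

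**What is serious, and who is told.** In 6.1.2 one criterion is "Requires in-patient hospitalisation or prolongation of existing hospitalisation"; a fatal event is another. Planned or disease-related admissions are not exempted. The section continues: "Serious adverse events will be reported to the Principal Investigator and the Sponsor", within 24 hours, and to the ethics committee within 72 hours. Section 8.6.2 repeats the 72-hour duty for any serious event.

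**What limits this.** Section 6.0 opens with "Not applicable to current protocol has no treatment or therapy is a consequence of planned actions". Sections 6.2.3 and 6.4.1 reserve expedited reporting for serious events that are both related and unexpected (Sponsor 24 hours, ethics committee 15 days). For each event the investigator must "make a causality assessment of the treatment using one of the four given definitions"; 6.2.2 asks the same for serious events against the trial treatment.

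**Cohort and follow-up.** The end of study is set at 20 years (4.7); the synopsis says the duration is indefinite. Follow-up sources in 4.5 include "Hospital episodes statistics (HES), and death registry formerly via Office for National Statistics, ONS", and 2.2 uses long-term follow-up to assess the prognostic value of biomarkers.

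**The concern.** Participants are hospital patients, including ventilated, trauma and cardiogenic-shock patients (1.5.2). Admissions and deaths are expected from their disease and are also the outcomes the registry follows. A capture rule with no link to a procedure and no window makes those events candidates for adverse-event forms until the study ends, and nothing in the text separates an outcome from an adverse event.

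The study does have procedures that could cause harm: an extra venepuncture when no clinical one is scheduled and tissue harvested at surgery (4.4), up to 50 ml of blood (5.2), up to 10 minutes of added scanning (1.1) and device evaluations (1.4). Section 6 names none of them as the exposure. Staff can find support in the text for recording everything, for reporting only related and unexpected events, or for treating the section as not applicable. Sections 1.4 and 1.5.2 state that risk is minimal, and inconsistent capture would leave that statement poorly supported.

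**Working it through.** **1. The protocol's own figure.** Section 4.7: 10 years of recruitment + at least 10 years of storage = 20 years. This reproduces. If accrual is uniform over the 10 years and the study ends at year 20, individual follow-up runs from 10 to 20 years, mean 15. Twenty years is therefore the maximum, reached by the earliest participants. Under the synopsis wording there is no upper limit.

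**2. The rules side by side.**

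| Section | Which events | Clock |
|---|---|---|
| 6.0 | section not applicable | none |
| 6.1.1 | all adverse events in the study | form, no window |
| 6.1.2, 8.6.2 | all serious events | Sponsor 24 h (6.1.2), ethics committee 72 h (both) |
| 6.2.3, 6.4.1 | related and unexpected serious events | Sponsor 24 h, ethics committee 15 days |
| Appendix 1 table | serious events, no filter stated | Sponsor 24 h, ethics committee 15 days |

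These cannot all be followed. The filter in 6.2.3 and 6.4.1 acts on reporting, after capture; it does not narrow what 6.1.1 puts on a form. Reconciling the clocks alone would leave the capture rule unchanged.

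**3. The causality question.** Sections 6.1.1 and 6.2.2 grade against a treatment, and 6.0 says there is none. A haematoma after a research blood draw therefore has no named exposure to be graded against.

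**4. Illustration of volume on the literal rule.** Inputs: N = 23,400 (2.1, recruited to date, taken here as the whole cohort); mean follow-up 15 years (step 1, ignoring deaths and withdrawals); r = 0.05 to 0.5 admissions or deaths per person-year, an **assumption**, since the protocol gives no rate.

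- Per year: N × r = 23,400 × 0.05 = 1,170, to 23,400 × 0.5 = 11,700.
- Per day: divided by 365.25, about 3 to 32.
- Over the study: 23,400 × 15 = 351,000 person-years at most; × r = 17,550 to 175,500 serious events.

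**5. Illustration of dilution.** Let q be the assumed proportion of participants with one procedure-related serious event.

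- Share without a window = Nq / (Nq + 351,000 r).
- Share with a window of d days after one procedure = Nq / (Nq + N r d / 365.25).

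Here d = 7 only shows what a window does; it is not a proposal.

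| q (assumed) | Related events | Share, no window | Share, d = 7 |
|---|---|---|---|
| 1 in 10,000 | 2.3 | 0.001% to 0.013% | 1% to 9% |
| 1 in 1,000 | 23.4 | 0.01% to 0.13% | 9% to 51% |
| 1 in 100 | 234 | 0.13% to 1.3% | 51% to 91% |

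At q = 1 in 1,000, misgrading unrelated events as related at a rate of only 23.4 / 175,500 = 0.013% to 23.4 / 17,550 = 0.13% would produce as many false related events as true ones.

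**The case against.** The strongest reply is that related harms can be retrieved. Every adverse event gets a four-level causality grade (6.1.1), every serious event a causality assessment (6.2.2), and related and unexpected ones are escalated (6.2.3, 6.4.1). A reader might infer from the capture rule that any harm from sampling would be buried; the protocol does not support that. A working causality field can pick out related events however many others surround them. What remains is dilution, together with a causality field worded against the wrong exposure.

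Other points also stand in part:

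- A reader might infer that every admission and death in the linked records must go on an adverse-event form. No section says so. Section 6.1.1 speaks of events encountered in the study, and the clocks in 6.4.1 and Appendix 1 run from learning of the event.
- A reader might infer from the definition in 6.1.1 that nobody can have an adverse event here, because no product is given. But the definition also names an intervention, which can cover a blood draw. Nor is the choice simply between all events and none: 6.1.3 limits non-serious events to those the investigator judges significant, and 6.4.1 gives a further reading.
- Section 5.2 mentions an adverse-event procedure within the sampling SOPs, and 8.2 lists an SAE reporting plan. Neither is shown, nor is the figure in Appendix 1. It cannot be said that harms go unrecorded.
- Safety endpoints are not applicable (7.3) and 8.6.12 requires no data safety monitoring plan, so the protocol promises no safety rate and need not be faulted for lacking one.

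None of this reconciles 6.0, 6.1.1, 6.1.2, 8.6.2 and 6.4.1, or gives the causality question an exposure.

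**Conclusion.** The point holds as a rule that the protocol states and that misfires in this cohort. Capture in 6.1.1 has no tie to a research procedure and no window; 6.1.2 and 8.6.2 attach unfiltered reporting duties to any admission or fatal event; 6.0, 6.2.3 and 6.4.1 say otherwise; and causality is graded against a treatment that does not exist. Procedure-related harm is diluted among disease events and lacks a defined exposure.

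The size is not fixed by the protocol. The 1,170 to 11,700 serious events a year, and the related share of 0.001% to 1.3% without a window, rest on assumed event rates, assumed procedure risks, uniform accrual, no attrition, and the literal reading that every admission and death is captured. If events found only through registries are not counted, or if the unseen SOP already limits capture, the volume is smaller. The contradiction between sections, and the missing exposure in Section 6, do not depend on any of these figures. The change is worth making because it costs little, but it does not call the registry's scientific use into question.

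**What to change.** 1. Reconcile 6.0, 6.1.1, 6.1.2, 8.6.2 and 6.4.1 so that one statement says whether Section 6 applies, which events are recorded, which are reported, to whom and by when. Align 6.2.3 and Appendix 1 with it. Which clock applies is for the sponsor to decide.
2. In 6.1.1 and 6.2.2, replace the treatment wording: the exposure, and the causality question, are the BBR research procedures (research blood draw, tissue or swab collection, added scan time, device evaluation).
3. Limit routine AE and SAE capture to events arising during such a procedure or within a window after it that the sponsor sets, plus any event at any time, from any source including linked records, that is judged possibly related to one.
4. State that other hospital episodes and deaths obtained through records or registries are follow-up outcomes and not adverse events. The exception for possibly related events in item 3 must stay: excluding all record-derived episodes would drop an admission caused by a tissue sample but found only through linkage.
5. Bring the sampling SOP (5.2) and the SAE reporting plan (8.2) into line.

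Cost: a protocol amendment and matching SOP edits. No new data are collected, and on the literal reading the workload falls. Downside: a late effect that nobody suspects is related would not be captured.
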